- Subjects with CLD/CHD \leq 24 months of age who were randomized to the palivizumab group for Season 1 will be re-randomized 1:1 to either the MEDI8897 group or the palivizumab group. Subjects in the MEDI8897 group will receive a single fixed IM dose of 200 mg MEDI8897 followed by 4 once-monthly IM doses of placebo (approximately 50 subjects). Subjects in the palivizumab group will receive 5 once-monthly IM doses of 15 mg/kg palivizumab (approximately 50 subjects).

In Season 1 or Season 2, subjects in the CLD/CHD cohort who undergo cardiac surgery with cardiopulmonary bypass after receipt of Dose 1 but prior to receipt of Dose 5 will receive a replacement dose of the study drug they received for Dose 1 immediately following the surgery when determined by the physician to be medically stable for an IM injection. Any subsequent doses of study drug will continue to be given according to the protocol-specified dosing schedule. See Section 3.1.2.3 for details on replacement dosing.

Subjects in the preterm cohort will be followed through 1 year after Season 1/Dose 1, and subjects in the CLD/CHD cohort will be followed through 1 year after Season 2/Dose 1. Subjects in the CLD/CHD cohort who receive a replacement dose in Season 2 will be followed through 1 year after the last replacement dose.

[figure not shown]
Subjects in the CLD/CHD cohort with a weight $<$ 7 kg at the time of dosing for Season 2 will have increased monitoring of adverse events (AEs). Any SAEs or Grade 3 or Grade 4 AEs that occur in the first month after dosing will be sent to the independent data monitoring committee for immediate review.

Subjects will be monitored throughout the study for LRTI (see Section 4.3.1). All subjects seeking medical attention for a respiratory illness (in either the inpatient or outpatient setting) will be evaluated for LRTI, including protocol-defined medically attended RSV LRTI (Table 7 and Table 8). All subjects evaluated for LRTI will have respiratory samples obtained and tested centrally for RSV using the United States Food and Drug Administration (US FDA)-cleared and *Conformité Européenne* (CE) or European Conformity-marked in vitro diagnostic real-time reverse transcriptase-polymerase chain reaction (RT-PCR) assay (see Section 4.3.1.2).

Blood samples will be collected for PK, ADA, and RSV neutralizing antibody and RSV serology as defined in Sections 4.3.3, 4.3.4, and 4.3.5, respectively.

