5.5.1 Time Period for Collection of Adverse Events

AEs and SAEs will be recorded from the time of signature of informed consent through the follow-up period (Day 361).

All AESIs and NOCDs will be recorded from the time of dosing with study drug through the follow-up period (Day 361).

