3.7 Safety Analyses

All safety analyses will be conducted on as-treated population.

For each season as well as the two consecutive seasons combined (ie, Season 1, Season 2, Season 1 + Season 2) the summaries will be provided using the respective as-treated population. The Season 1 summaries will also be provided for each cohort (pre-term, CHD/CLD).

For each season, all safety analyses planned will be presented. For Season 1 + Season 2, number and percentage of subjects with treatment-emergent adverse events (TEAEs), treatment-emergent serious adverse events (TESAEs), adverse events of special interest (AESIs), IP-related skin reactions, and new onset chronic diseases (NOCDs) will be summarized by MedDRA System Organ Class (SOC) and Preterm Term (PT) for palivizumab/palivizumab and MEDI88987/MEDI8897 groups. The Season 1 + Season 2 summaries will be presented for CLD/CHD cohort, for CLD subjects and CHD subjects, separately.

For Season 2 summaries and Season 1 + Season 2 summaries, direct comparison between MEDI8897/MEDI8897 with palivizumab/palivizumab groups are subject to potential bias if the dropouts of Season 1 are associated with safety.

 Table 3
 Reporting Period of Treatment-emergent Adverse Events

Reporting Period	Definition of Treatment-emergent AEs	
Season 1	Any AEs that started on/after date of 1 st dose of Season 1, and prior to the end of Season 1, Day 361 or the last day prior to 1 st dose of Season 2, whichever comes earlier.	
Season 2	Any AEs that started on/after date of 1st dose of Season 2 and prior to the end of Season 2, Day 361.	
Season 1 + Season 2	Any AEs that started on/after date of 1st dose of Season 1 and prior to the end of Season 2, Day 361.	

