3.7.1 Adverse Events and Serious Adverse Events

Adverse events and serious adverse events will be coded by MedDRA version 22 or higher and the type, incidence, severity and relationship to study investigational product will be summarized by treatment group. Specific AEs will be counted once for each subject for calculating percentages. In addition, the total number of AEs will also be provided. In addition, if the same AE occurs multiple times within a particular subject, the highest severity and level of relationship observed will be reported. All treatment-emergent AEs (TEAEs) and treatment-emergent SAEs (TESAEs) occurring through Day 361 will be summarized overall, as well as categorized by MedDRA SOC and PT. In addition, the TEAEs occurring at 1% or higher in either treatment group will be reported by PT.

Nontreatment-emergent AEs/serious adverse events (SAEs), defined as AEs/SAEs that occur prior to the administration of investigational product, or after Day 361, Season 1 for preterm cohort, or after Day 361, Season 1 and prior to Day 1, Season 2 for CHD/CLD cohort, or after Day 361, Season 2 for CHD/CLD cohort, or pre-planned surgeries that are coded with PT "Cardiac Operation" and occur during the study for CHD subjects will be presented in the listings.

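### Adverse events after Season 2 Day 361 in children re-dosed after bypass surgery are followed under the protocol but fall outside the SAP's treatment-emergent window

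*SAP*

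**What the plan says.** **Follow-up.** Protocol 3.1.1 states: "Subjects in the CLD/CHD cohort who receive a replacement dose in Season 2 will be followed through 1 year after the last replacement dose". SAP 2.2 repeats this. Protocol Table 6 gives these children a dedicated visit 360 days after the last replacement dose, marked for AE/SAE, AESI and NOCD assessment, with telephone calls continuing on the same schedule.

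**Recording.** Protocol 5.5.1 says "AEs and SAEs will be recorded from the time of signature of informed consent through the follow-up period (Day 361" and gives the same end day for AESIs and NOCDs. It makes no exception for replacement doses.

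**Analysis.** In SAP Table 3 the Season 2 row takes AEs that "started on/after date of 1st dose of Season 2 and prior to the end of Season 2, Day 361". The Season 1 + Season 2 row takes AEs that "started on/after date of 1st dose of Season 1 and prior to the end of Season 2, Day 361". SAP 3.7.1 sets the scope of the tables: "All treatment-emergent AEs (TEAEs) and treatment-emergent SAEs (TESAEs) occurring through Day 361 will be summarized overall". It treats as nontreatment-emergent, and only lists, AEs and SAEs that occur "after Day 361, Season 1 and prior to Day 1, Season 2 for CHD/CLD cohort, or after Day 361, Season 2 for CHD/CLD cohort".

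**Purpose.** TEAEs, TESAEs, AESIs and NOCDs are the primary endpoint (Protocol 2.1). Protocol 3.2.3 names two sources of safety data on more than one MEDI8897 dose: children dosed in both seasons, and children given a replacement dose.

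**The concern.** The protocol extends follow-up because a child has been dosed again, but the SAP's window is anchored to the season's first dose and does not move. A MEDI8897 child with no replacement dose has the full 360 days after the Season 2 active dose inside the window. A child re-dosed on Day 120 has 361 − 120 = 241 days. The more heavily exposed child therefore has the shorter counted follow-up, and the part lost is the late part, where an NOCD or a late SAE would appear.

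The recording conflict matters more than the tabulation. A site that follows Protocol 5.5.1 literally could stop recording at Day 361 although Table 6 calls for assessment later. A table can be rerun, but events that were never recorded cannot be recovered at analysis.

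There is also a definitional conflict between the seasons. The same event can be treatment-emergent under Table 3's combined row and nontreatment-emergent under 3.7.1, so two programmers could produce different Season 1 + Season 2 counts.

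**Working it through.** The documents give no figure for the length of this gap. Their one safety sample-size figure does reproduce: 1 − 0.995^600 = 0.951, against the stated 95% probability of at least one event at a true rate of 0.5%. That figure concerns Season 1 exposure, and nothing below changes it.

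**Inputs**
- Window end: Season 2 Day 361, read as inclusive (SAP Table 3).
- Follow-up end: 360 days after the last replacement dose (Protocol Table 6).
- Eligible surgery: after Dose 1 (Day 1) and before Dose 5, scheduled for Day 121 ± 2 (Protocol 3.1.2.3 and Table 6).

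**Formula.** For a last replacement dose on Season 2 Day d, follow-up ends on Day d + 360. Days after the dose that are counted: 361 − d. Days followed but not counted: (d + 360) − 361 = d − 1.

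| d | Follow-up ends | Counted (361 − d) | Not counted (d − 1) | Share of 360 |
|---|---|---|---|---|
| 31 | Day 391 | 330 | 30 | 8% |
| 60 | Day 420 | 301 | 59 | 16% |
| 90 | Day 450 | 271 | 89 | 25% |
| 120 | Day 480 | 241 | 119 | 33% |
| 123 | Day 483 | 238 | 122 | 34% |

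Day 123 is not a strict maximum. The Dose 5 limit applies to the surgery, and the replacement dose waits until the child is judged stable for an injection, so a delay lengthens the tail day for day.

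**Between-season events.** Suppose Season 2 Dose 1 falls after Season 1 Day 361 and an AE starts in between.
- Table 3, Season 1 row: excluded, because the row stops at the earlier of Day 361 and the day before Season 2 Dose 1.
- Table 3, Season 2 row: excluded, because it precedes Season 2 Dose 1.
- Table 3, Season 1 + Season 2 row: included.
- SAP 3.7.1: nontreatment-emergent and listed, with no statement of which summary this applies to.

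SAP 3.7 presents the combined summary only for palivizumab/palivizumab and MEDI8897/MEDI8897. A gap event in a palivizumab/MEDI8897 child therefore appears only in the listing.

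**The case against.** The case on the other side is substantial, and most of it limits the size of the problem.

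- **Most post-replacement follow-up is counted.** A reader might infer that the whole year after any replacement dose is lost. The documents do not support that. Only Season 2 replacement doses carry extended follow-up, and only events after Season 2 Day 361 fall outside. For a Day 120 dose about two thirds of the 360 days is counted.
- **Repeat-dose safety is tabulated.** SAP 3.7.5 summarizes TEAEs, TESAEs, AESIs and IP-related skin reactions by number of active doses beyond plan, and assigns AEs near a replacement dose to that dose. This stands, although NOCDs are not in that summary. Later AEs are listed, so to call them removed from the analysis would go too far; they are left out of the summary tables.
- **AESIs and NOCDs have no cut-off of their own.** SAP 3.7.2 and 3.7.4 are silent, so their late handling is undefined rather than expressly excluded. The AESIs that Protocol 5.3 describes as occurring around dosing, or within 1 to 2 weeks of first exposure, would mostly fall inside the window anyway.
- **Protocol 5.5.1 may be shorthand.** It refers to the follow-up period, and Table 6 places the replacement-dose visit within that period. This reading is possible, but the stated end day is explicit and should not need interpretation.
- **A common window has merit.** The safety tables are crude percentages. Extending the window only for surgical children would mix about 361 and about 480 days in one denominator. This stands, and it shapes the fix.
- **The gap may not arise.** Protocol Table 5 allows Season 1 Day 361 and Season 2 Day 1 to be the same visit. Where a gap exists, event dates identify the events, so the combined counts can be reconciled. The wording conflict remains.

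**Conclusion.** The point holds in a limited form. In children given a replacement dose in Season 2, AEs that start after Season 2 Day 361 but within 360 days of the last replacement dose are followed under the protocol, classed as nontreatment-emergent by the SAP, and only listed. Protocol 5.5.1 conflicts with Table 6 on whether they are recorded at all. The tail is d − 1 days per child, about a third of the 360 days for a dose near Day 120, and longer if dosing is delayed after surgery.

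The documents do not state how many children will be re-dosed in Season 2, so the number of events affected cannot be calculated. It is probably small: these are children having bypass surgery between Dose 1 and Dose 5 of one season, within a cohort of about 300. A reader might also infer that the planned primary analysis is affected. It is not, since it uses Season 1 data only; the Season 2 and combined-season safety summaries are the ones concerned. The between-season conflict is a separate and smaller inconsistency.

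This does not threaten the trial's main safety comparison. It is worth correcting because it concerns primary-endpoint events in children on whom the protocol relies for repeat-dose safety.

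**What to change.** 1. **Protocol 5.5.1.** State that AEs, SAEs, AESIs and NOCDs are recorded through Day 361 or, for children given a Season 2 replacement dose, through 360 days after the last replacement dose if that is later. This matches Table 6 and is the part to settle first, while these children are still in follow-up.
2. **SAP Table 3 and 3.7.1.** Class events up to 360 days after the last Season 2 replacement dose as treatment-emergent. Keep the common tables at Day 361, and add one TEAE/TESAE/AESI/NOCD summary by treatment group for replacement-dose children through the end of their follow-up. Unequal follow-up is then not mixed in one percentage.
3. **SAP 3.7.1, between-season events.** State that the exclusion applies to the single-season summaries only, that these events count in the Season 1 + Season 2 summary, and that they stay listed for every group. Simply deleting the exclusion would leave gap events in palivizumab/MEDI8897 children in no summary and no such listing.

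The cost is one extra summary table, some SAP wording and a one-line protocol clarification. The visits and assessments are already scheduled.

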3.7.1 Adverse Events and Serious Adverse Events

Adverse events and serious adverse events will be coded by MedDRA version 22 or higher and the type, incidence, severity and relationship to study investigational product will be summarized by treatment group. Specific AEs will be counted once for each subject for calculating percentages. In addition, the total number of AEs will also be provided. In addition, if the same AE occurs multiple times within a particular subject, the highest severity and level of relationship observed will be reported. All treatment-emergent AEs (TEAEs) and treatment-emergent SAEs (TESAEs) occurring through Day 361 will be summarized overall, as well as categorized by MedDRA SOC and PT. In addition, the TEAEs occurring at 1% or higher in either treatment group will be reported by PT.

Nontreatment-emergent AEs/serious adverse events (SAEs), defined as AEs/SAEs that occur prior to the administration of investigational product, or after Day 361, Season 1 for preterm cohort, or after Day 361, Season 1 and prior to Day 1, Season 2 for CHD/CLD cohort, or after Day 361, Season 2 for CHD/CLD cohort, or pre-planned surgeries that are coded with PT "Cardiac Operation" and occur during the study for CHD subjects will be presented in the listings.

3.7.2 Adverse Events of Special Interest

Adverse events of special interest (AESI) will include targeted AEs of anaphylaxis and other serious hypersensitivity reactions including immune complex disease and AEs of thrombocytopenia. The number and percentage of subjects with AESIs will be summarized by treatment group and by SOC and PT.

Of note, investigators have been requested to identify the AESI in reporting. The primary interpretation of data will be made upon those events with investigator assessment. In addition, a supplementary analysis is conducted which runs the narrow Standardised MedDRA Query (SMQ) for hypersensitivity, the narrow and broad SMQ for anaphylactic reaction, and a study specific query based on compatible PTs for thrombocytopenia and immune complex disease occurring in the database. These SMQs and PTs will be provided by the medical monitor in a separate document before DBL for Primary Analysis.

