Overall, the incidence of investigational product-related TEAEs (MEDI8897 2.3%, placebo 2.1%); adverse events of special interest (AESIs), including hypersensitivity, immune complex disease, and thrombocytopenia (MEDI8897 0.5%, placebo 0.6%); and new onset chronic diseases [REDACTED] was low and generally comparable between the placebo and MEDI8897 groups. AESIs were reported in 5 subjects (4 subjects with rash or rash macular and 1 subject with petechiae) in the MEDI8897 group and 3 subjects (rash or rash papular) in the placebo group. All events were Grade 1 in severity. The TEAE of petechiae that was reported as an AESI was 1-day duration and was reported by the site investigator based on description by the parent. There were no laboratory assessments for the petechiae.

TEAEs that involved the skin and subcutaneous tissues (including diaper rash) were collected as skin reactions, with a few exceptions for skin reactions that could be definitively diagnosed such as impetigo, varicella, and scabies. [REDACTED]

Following a single fixed 50-mg IM dose of MEDI8897, over 95% of measurable Day 151 concentrations were greater than the nonclinical EC₉₀ target of 6.8 µg/mL. The median area under the concentration-time curve from time 0 to infinity (AUC_{0-∞}) and estimated apparent t_{1/2} were 5.3 day.mg/mL (range, 3.2 to 10.2 day.mg/mL) and 56.5 days (range, 46.8 to 81.1 days), respectively.

Overall, the rate and titers of ADA were low, and in ADA-positive subjects there was no effect on PK or safety. Of the subjects who had serum samples available for testing, ADA was detected post baseline in 4.3% (40/921) of subjects in the MEDI8897 group and 2.8% (13/466) of subjects in the placebo group; with less than 5% of subjects in either group being ADA positive at any visit. ADA titers ranged from 1:50 to 1:3,200 in the MEDI8897 group and 1:50 to 1:200 in the placebo group. Of the MEDI8897 subjects who were post-baseline ADA positive, ADA targeting the YTE domain was observed in 4/17 subjects on Day 151 and 10/15 on Day 361. Two MEDI8897 subjects had ADA on Day 361.

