2 OBJECTIVES AND ENDPOINTS

2.1 Primary Objective and Associated Endpoint

Table 1 Primary Objective and Associated Endpoint

Type	Objective	Endpoint
Safety	To evaluate the safety and tolerability of MEDI8897 compared to palivizumab when administered to preterm infants entering their first RSV season and children with CLD or CHD entering their first and second RSV season	Safety and tolerability of MEDI8897 as assessed by the occurrence of all TEAEs, TESAEs, AESIs, and NOCDs

AESI = adverse event of special interest; CHD = congenital heart disease; CLD = chronic lung disease; NOCD = new onset chronic disease; RSV = respiratory syncytial virus; TEAE = treatment-emergent adverse event; TESAE = treatment-emergent serious adverse event.

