4.8.3 Safety

4.8.3.1 Analysis of Adverse Events

AEs will be graded according to the current version of the NCI CTCAE where applicable for pediatric assessments. AEs will be coded by the Medical Dictionary for Regulatory Activities and the type, incidence, severity, and relationship to study drug will be summarized by treatment group. Other safety assessments will include the occurrence of AESIs defined as AEs of hypersensitivity to study drug (including anaphylaxis), thrombocytopenia, and immune complex disease (eg, vasculitis, endocarditis, neuritis, glomerulonephritis) following study drug administration, and the occurrence of NOCDs following study drug administration.

Safety of MEDI8897 will be summarized by treatment group based on the ATP. The safety summary will be provided for each season, as well as for the 2 consecutive RSV seasons (ie, Season 1 and Season 2). For the Season 1 summary, the analysis dataset will include subjects from the preterm cohort and CLD/CHD cohort, presented by the treatment received in Season 1; for the Season 2 summary and the 2 consecutive-season summary, the analysis dataset will include subjects from the CLD/CHD cohort, presented by the treatment received through the 2 seasons.

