5.3 Definition of Adverse Events of Special Interest

An AESI is one of scientific and medical interest specific to understanding of the investigational product and may require close monitoring and rapid communication by the investigator to MedImmune. An AESI may be serious or nonserious. The rapid reporting of AESIs allows ongoing surveillance of these events in order to characterize and understand them in association with the use of this investigational product.

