5.3.1 Hypersensitivity, Including Anaphylaxis

Administration of polyclonal immunoglobulin preparations and mAbs has been associated with immediate (type I) hypersensitivity (including anaphylaxis) that occurs during or after dosing. An immediate hypersensitivity reaction is defined as an acute onset of an illness with involvement of the skin, mucosal tissue, or both during administration of investigational product (but does not meet the definition of anaphylaxis). Anaphylaxis is a rare event, usually occurring after subsequent exposure to antigen, and it is most commonly accompanied by severe systemic skin and or mucosal reactions. It is potentially a fatal, systemic allergic reaction that is distinct from simple allergic reactions (eg, rash, pruritus) because of the simultaneous involvement of several organ systems (Sampson et al, 2006). A full definition of anaphylaxis is provided in [Appendix B](#). See Section 5.5 for recording AEs.

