5.7.3 Adverse Events of Special Interest

5.7.3.1 Hypersensitivity, Including Anaphylaxis

Events of immediate (type I) hypersensitivity, including anaphylaxis (as defined in [Appendix B](#)), require that the investigator or other site personnel inform appropriate sponsor study representatives immediately, or **no later than 24 hours** of when he or she becomes aware of the event. The designated sponsor study representative works with the investigator to ensure that all relevant information is provided and entered in EDC. If the event is considered serious it must be reported as an SAE (see Section 5.6).

Signs of immediate hypersensitivity include urticaria, pruritus, angioedema, skin rash, difficulty breathing, and wheezing. Parent(s)/legal representatives will be provided a card with this information to aid in prompt identification and reporting of these signs. Parent(s)/legal representatives will be instructed to immediately report the occurrence of any of these findings to the site investigator who should then report the events to appropriate sponsor study representatives immediately, or **no later than 24 hours** of when he or she becomes aware of the event.

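### SAP 3.7.2 limits hypersensitivity AESIs to serious events where the protocol does not, and leaves open whether investigator-flagged nonserious events are counted

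*SAP*

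**What the plan says.** Protocol 2.1 gives the primary endpoint as "Safety and tolerability of MEDI8897 as assessed by the occurrence of all TEAEs, TESAEs, AESIs, and NOCDs". Protocol 4.8.3.1 then describes "AESIs defined as AEs of hypersensitivity to study drug (including anaphylaxis), thrombocytopenia, and immune complex disease", with no seriousness condition. Protocol 5.3 is explicit: "An AESI may be serious or nonserious". For recognising cases, Protocol 5.7.3.1 states: "Signs of immediate hypersensitivity include urticaria, pruritus, angioedema, skin rash, difficulty breathing, and wheezing".

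SAP 3.7.2 describes AESIs as "targeted AEs of anaphylaxis and other serious hypersensitivity reactions including immune complex disease and AEs of thrombocytopenia". As the phrase is built, *serious* governs the hypersensitivity reactions other than anaphylaxis and, through them, immune complex disease. Thrombocytopenia carries no such condition.

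The same SAP section says that investigators identify AESIs when reporting and that the primary interpretation rests on investigator-assessed events. It adds a supplementary search by SMQ and preferred term, for which no seriousness filter is stated. The SAP amendment history records that the AESI definition was changed to match the Safety Strategy and Management Plan, which is not among the documents reviewed.

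Protocol Amendment 1 is dated 31 March 2021 and SAP version 2.0 is dated 5 April 2021. Both texts are current.

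**The concern.** The two documents define one component of the primary endpoint differently. Sites work to the protocol, so a nonserious rash thought to be hypersensitivity can properly be flagged as an AESI. At analysis there are two ways to treat it. Either it is counted, and the SAP's definition is not followed, or it is dropped, and the protocol's definition is not followed. The SAP does not choose.

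The gap affects more than one table. Under SAP 3.7 and 3.7.5, AESIs are summarised for each season and for both seasons combined, and by age, weight on Day 1, timing relative to dosing and number of active doses. If the literal wording were programmed, the main AESI tables would follow a narrower definition than the one under which events were collected.

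**Working it through.** **Definitions side by side**

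- Hypersensitivity other than anaphylaxis: the protocol includes serious and nonserious events; the SAP, read literally, includes serious events only.
- Immune complex disease: the protocol includes serious and nonserious events; the SAP, read literally, includes serious events only.
- Anaphylaxis: included in both.
- Thrombocytopenia: included in both, without a seriousness condition.

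**The plan's own safety figures**

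Protocol 4.8.2 and SAP 2.4 state a 95% probability of at least one AE among 600 MEDI8897 subjects at a true rate of 0.5%.

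- 1 − (1 − 0.005)^600 = 0.9506, which agrees.
- With no events in 600, the exact one-sided 95% upper limit is 1 − 0.05^(1/600) = 0.498%, which agrees with the stated bound of below 0.5%.

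**Phase 2b inputs (Protocol 1.4.1)**

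The numbers dosed were 966 (MEDI8897) and 481 (placebo). On MEDI8897, "AESIs were reported in 5 subjects (4 subjects with rash or rash macular and 1 subject with petechiae) in the MEDI8897 group". On placebo there were "3 subjects (rash or rash papular) in the placebo group". All were Grade 1.

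- 5/966 = 0.52% (stated as 0.5%).
- 3/481 = 0.62% (stated as 0.6%).
- Rash subjects: 4 + 3 = 7 of 8.

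**Illustration for 600 MEDI8897 subjects**

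This rests on two assumptions: none of the Phase 2b rashes met a seriousness criterion, and the Phase 2b rate carries over. Expected count = 600 × x/966, and P(at least one) = 1 − (1 − x/966)^600.

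- Protocol definition, x = 5: expected 3.1; P = 95.6%. The exact 95% interval for 5/966 is 0.168% to 1.204%, so the expected count ranges from 600 × 0.00168 = 1.0 to 600 × 0.01204 = 7.2.
- SAP wording read literally, with petechiae accepted as thrombocytopenia, x = 1: expected 0.6; P = 46.3%.
- SAP wording read literally, with petechiae not accepted, x = 0: expected 0.

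**Sensitivity to the seriousness assumption**

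If k of the 4 MEDI8897 rashes had been serious and the petechiae is kept, the literal wording retains x = 1 + k. The expected count in 600 is then 0.6, 1.2, 1.9, 2.5 or 3.1 for k = 0, 1, 2, 3 or 4. The difference between the definitions disappears only at k = 4.

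**Where an excluded event would still appear**

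- TEAE tables by SOC, preferred term and severity (SAP 3.7.1): yes, but not identified as an AESI.
- Supplementary SMQ and preferred-term analysis (SAP 3.7.2): yes, if it matches the query.
- Skin-reaction table (SAP 3.7.3): only if it was reported on the dedicated form and judged related to the product.

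**The case against.** The best defence is that the only operating rule in SAP 3.7.2 is the reliance on investigator-identified events. No sentence tells the programmer to remove a flagged event because it is nonserious, so the main table may well count them all. All TEAEs also belong to the primary endpoint, so no event vanishes from it. The wording applies equally to both arms, and SAP 1 rules out formal testing of safety. The change of definition was documented, and how the Safety Strategy and Management Plan uses the word cannot be checked here. All of this stands. It makes loss of events a risk rather than a certainty. It does not remove the conflict, because a definition and a counting rule that point different ways still need one sentence to join them.

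A reader might infer that no AESI of the kind seen in Phase 2b could qualify under the SAP, or that the AESI table is bound to look cleaner than it should. The documents do not support either.

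- The petechiae falls most naturally under thrombocytopenia, which the SAP leaves unrestricted. Whether it qualifies is uncertain because no laboratory assessment was made and Protocol 5.7.3.3 refers to a platelet count below 120,000 per µL.
- Protocol 1.4.1 reports severity grade, not seriousness, and Appendix A keeps the two apart. That the rashes were nonserious is likely but not stated.
- Phase 2b enrolled healthy preterm infants given one injection. This trial enrols high-risk infants given five. The expected counts are illustrations, not forecasts.

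**Conclusion.** The point holds as a current conflict between protocol and SAP over a component of the primary endpoint, joined to an unstated counting rule. It does not hold as a demonstrated loss of safety data.

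On the literal reading, and under the two assumptions above, 7 of 8 Phase 2b AESI subjects would be excluded (4 of 5 on MEDI8897 and 3 of 3 on placebo). The expected MEDI8897 count in 600 would fall from about 3 (roughly 1 to 7) to about 0.6 or none. If every investigator flag is counted, the effect is nil. The SAP should say which applies before database lock.

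A separate and minor point concerns Protocol 5.3.1. It describes an immediate reaction as an acute illness "with involvement of the skin, mucosal tissue, or both during administration of investigational product", while the sentence before it also allows onset after dosing. No effect on data capture is shown: Protocol 5.5.1 records AESIs from dosing to Day 361, Protocol 5.7.3.1 sets no onset limit on reportable signs, and Protocol 4.3.7 collects skin reactions whatever their onset time.

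**What to change.** In SAP 3.7.2, before database lock for the primary analysis:

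1. Restore the protocol definition: hypersensitivity including anaphylaxis, immune complex disease and thrombocytopenia, serious or nonserious.
2. State that all investigator-identified AESIs are counted in the main AESI table. This is the sentence that settles the ambiguity.
3. Show serious AESIs as a sub-row, so that the narrower view remains visible.

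Separately, reconcile the two descriptions of onset in Protocol 5.3.1.

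The cost is a few lines of SAP text, one extra row in the AESI tables and a short protocol clarification. No new data are needed, since seriousness is already assessed for every AE under Protocol 5.5. The reported AESI count may be somewhat higher than a literal reading of the present wording would give.
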